12.0 RECORDS AND REPORTING

See the Case Report Forms posted on the COG web site with each protocol under “*Data Collection/Specimens*”. A submission schedule is included.

12.1 CDUS

This study will be monitored by the Clinical Data Update System (CDUS). Cumulative CDUS data will be submitted quarterly to CTEP by electronic means. Reports are due January 31, April 30, July 31 and October 31. This is not a responsibility of institutions participating in this trial.

13.0 PATHOLOGY GUIDELINES AND REQUIREMENTS

13.1 Review of Diagnostic CSF for CNS Disease Patients

For patients who are diagnosed with CNS disease based on blasts in the CSF, we strongly recommend that you contact the COG APL investigator [name] to discuss central review of the CSF slides. [name] can be contacted at [contact] and he will provide shipping information upon contact.

13.2 Review of End Induction Bone Marrow

Optional Pathology Consultation

In some cases the local pathologist may have difficulty or need a second opinion interpreting the marrow status at the end of Induction. If a consultation for a difficult case is desired then this would be arranged on a consultation basis only and a fee may be charged. If a consultation is desired, the institution may send pathology materials (stained and unstained slides from bone marrow and peripheral blood and pathology, bone marrow, flow cytometry reports including copies of blast gate and dot plots of markers) and pertinent cytogenetics data to the study pathologist. Please contact the study pathologist to request a consult and verify what is needed for the consultation prior to submitting pathology materials.

Copies of consult reports will be sent to contributing institution and study chair, in order to include them in study data files.

Materials sent for consultation must be shipped using the institution’s courier account to:

AAML1331 Study Review Pathologist
[name]
Department of Pathology
Nationwide Children’s Hospital
[name]
[name]
[contact]
[contact]
Email: [contact]

14.0 CYTOGENETIC ANALYSIS GUIDELINES AND REQUIREMENTS

14.1 Cytogenetic Analysis Overview

It is strongly recommended that all patients enrolled on AAML1331 have a cytogenetics/FISH PML-RAR α study performed by a COG approved laboratory at the time of initial diagnosis and relapse.

The institutional CRA must inform the cytogenetics laboratory that the patient has been enrolled in a COG APL study and that the cytogenetics/FISH data must be **submitted within 2 weeks of enrollment** on the AAML1331 protocol. See [Appendix V](#) for cytogenetics procedures and for the Study Authorization Form for reflexive FISH testing.

14.2 Specimen Collection and Submission

It is strongly recommended that specimens for cytogenetic/FISH PML-RAR α analysis be sent to a COG approved institutional cytogenetics laboratory. If a COG institution does not have a COG approved laboratory, the institution may send the samples for karyotyping/FISH studies to any COG approved cytogenetics laboratory on a fee-for-service basis. Prior arrangements for performing cytogenetics and/or FISH studies should be made with the laboratory. An authorization form for the reflexive FISH testing signed and dated (by the physician or designees just as with any order) and sent to the cytogenetics laboratory with the sample will simplify and enhance the ability to obtain FISH testing and results.

14.2.1 Specimen Collection

A minimum of 2 mL (optimal volume is 3 mL) of fresh whole bone marrow aspirated through a needle into a syringe containing sodium heparin (preservative-free is preferable) is recommended in all cases. A first or second draw, or a draw from a repositioned needle, is best to ensure a sufficient number of leukemic cells in the aspirate. The specimens should be kept at **room temperature** and transported to the institutional cytogenetics laboratory as quickly as possible (**always within 24 hours of collection**). If shipping is done by overnight courier to an approved laboratory, that laboratory should be contacted to obtain instructions on transport. Some laboratories request that specimens be transferred in a 15 mL conical tube filled with RPMI - 1640 and 15% heat inactivated fetal calf serum. Specimens should be kept at ambient temperature.

14.2.1.1 If bone marrow cannot be aspirated, a trephine biopsy should be submitted. Also if available, 1 - 2 unstained bone marrow aspirate slide(s) can be used for FISH with PML-RAR α probes to confirm the diagnosis.

14.2.1.2 Peripheral blood (3 - 5 mL) collected in sodium heparin should be submitted as a back-up to the bone marrow when the marrow sample is suboptimal or unobtainable, if more than 20% circulating blasts are identified, or when a constitutional abnormality (e.g., trisomy 21) is a possibility.

Please note: Results of these studies should be submitted to the corresponding coordinator of the COG Myeloid Cytogenetics Committee for central review (see below).

14.2.2 Requirements for Data Submission

The following are required for each case: a completed COG Cytogenetics/FISH PML-RAR α Reporting Form (found on the COG member website) and two original karyotypes (different cells), with corresponding full size metaphase spreads of each abnormal clone or two karyotypes of normal cells with corresponding full size metaphase spreads in the case of normal cytogenetic analysis. A normal karyotype in the leukemic cells of a patient with APL could be

due to a cryptic insertion/rearrangement that would be detected by FISH with PML-RAR α probes. In such cases a sequential G-banded metaphase to FISH, or reverse DAPI on a metaphase should be performed to aid the localization of the probes. In very rare instances an evaluation of the case using a RAR α break apart probe may be required. This information must be sent to the appropriate coordinating cytogeneticist **within 2 weeks of enrollment on the AAML1331 protocol** (see [Appendix V](#)) and within one month of disease relapse, if applicable. Reports must be sent electronically. Reporting Cytogenetics forms must be filled out for all cases, whether or not the cytogenetic analyses were successful. A separate form is required for each specimen (i.e., bone marrow and blood) analyzed. FISH form, using the PML-RAR α probe, should also be completed and sent to the coordinating cytogeneticist with images documenting the abnormal or normal (in rare instances) FISH patterns. If the laboratory is not able to perform FISH, contact the COG cytogenetic coordinators for advice. Any discrepancies in interpretation between cytogenetics/FISH results from the laboratory and the coordinator will be discussed between the coordinators, with consult of additional cytogenetics committee members as necessary. The COG cytogenetics committee decision will be used for data analysis of trial results related to cytogenetic classification.

Cytogenetic Coordinators

Please send above materials by **e-mail** to the following COG Cytogenetics Laboratories:

WEST OF MISSISSIPPI RIVER
(INCLUDE MINNESOTA AND WISCONSIN), AUSTRALIA, NEW ZEALAND, WESTERN CANADA

SEND TO:

[name]

Director of Cytogenetics Laboratory
Department of Laboratory Medicine and Pathology

University of Minnesota

[name]

[name]

[name]

USA

[contact]

[contact]

E-mail: [contact]

EAST OF MISSISSIPPI RIVER
(EXCLUDE MINNESOTA AND WISCONSIN), EUROPE, EAST CANADA

SEND TO:

[name], FACMG

15.0 SPECIAL STUDIES SPECIMEN REQUIREMENTS

The exploratory studies detailed in this section are for research purposes only, and results will not be used to make clinical treatment decisions. Thus, results will not be obtained in real-time (but rather batched for retrospective review) and results will not be returned to the treating physician.

Please note, if there is an inadequate amount of bone marrow or blood for all optional studies, the studies should be prioritized in the following order:

1. Bone Marrow and Peripheral Blood Minimal Residual Disease Testing (see [Section 15.2](#))
2. Early Death and Coagulopathy Complications in Pediatric APL (see [Section 15.3](#))
3. Specimen Banking and FLT3 Mutations in Pediatric APL (see [Section 15.1](#))

Additionally, if patient/parent/responsible party consents, any specimens left over on this study after required tests are performed will be banked for future research studies.

Optional Biology Specimens	Diagnosis	Induction	Consolidation Cycle 2	End of Therapy	Relapse
FLT3 Study (Section 15.1)	X		X (Day 43)		X
MRD Study (Section 15.2)	X	X (Day 29)	X	X	X
Coagulopathy Study (Section 15.3)	X	X (Days 1, 8, 15, 29)			

15.1 FLT3 Mutations in Pediatric APL

15.1.1 Specimens

From consenting patients, 1 mL to 3 mL of bone marrow specimen will be collected at the following time points:

- At diagnosis. If bone marrow is not obtained at diagnosis, may submit 3 to 10 mL of peripheral blood instead. When APEC14B1 opens to AML patients, this diagnostic specimen will be collected through enrollment on APEC14B1.
- Day 43 of Consolidation Cycle 2
- At the time of either a molecular or morphologic relapse, if applicable.

15.1.2 Preparation

Bone marrow (1 - 3mL) must be obtained in purple top tube (EDTA tube). If unable to obtain bone marrow, may send peripheral blood (3 - 10 mL) in purple top tubes (EDTA tube). Samples may be stored at room temperature if shipped on the day of collection. If stored for longer, please refrigerate. If the sample is stored for longer than 24 hours, please add equal volume of RPMI medium (1 mL RPMI for 1 mL of specimen).

Utilize AML Specimen Transmittal forms specific for AAML1331. Specimens should be placed inside a leak proof biohazard envelope with absorbent material and then a pressure resistance Tyvek envelope as per IATA regulations. Blood and

marrow should be shipped in a shipping container with an Exempt Human Specimen label.

15.1.3 Labeling

Label the tubes with COG patient ID number, patient name and date of birth, date and time of collection, time point (include treatment cycle and day of cycle), and source of material (i.e., bone marrow or blood).

15.1.5 Detection of FLT3 Mutations

FLT3 mutation testing will be performed in the laboratory of [name] (Seattle, WA). [name] has an NIH R01 grant to study the role of FLT3 mutations in myeloid disease.

Genomic DNA is used to amplify exon 14/15 and exon 20 of the FLT3 gene using duplex PCR with specifically designed primers. The amplified products will be subjected to EcoRV digestion, capillary electrophoresis and GenScan analysis for identification of FLT3-ITD as well as FLT3 activation loop mutations (FLT3-ALM)⁷³. FLT3-ITD allelic ratio (ITD-AR) is determined as a ratio of mutant to normal product. Presence of FLT3-ALM and FLT3-ITD at various ITD-ARs will be correlated with clinical characteristics and outcome (on a retrospective research basis).

15.2 **Bone Marrow and Peripheral Blood Minimal Residual Disease (MRD) Testing**

Note: This optional research sample is different than the required RQ-PCR of PML-RARα research saclinical reasons which should be sent to an approved CLIA certified lab at time points indicated in the protocol. See [Section 7.1](#) for details.

15.2.1 Specimens

From consenting patients, 1 to 3 mL of bone marrow and 5 mL of peripheral blood will be obtained at the following timepoints to perform research evaluation of MRD. These samples are for research only and results will not be returned to the institution.

- At diagnosis (If bone marrow is not obtained at diagnosis, may submit peripheral blood only.)
- Induction Day 29
- Consolidation Cycle 2 Day 43 (and repeated 1-2 weeks later if positive)
- At the end of therapy
- At the time of either a molecular or morphologic relapse, if applicable

15.2.2 Preparation

Bone marrow (1 - 3mL) and peripheral blood (5 mL) must be obtained in purple top tubes (EDTA tubes). Samples may be stored at room temperature. Utilize AML Specimen Transmittal forms specific for AAML1331. Specimens should be placed inside a leak proof biohazard envelope with absorbent material and then a pressure resistance Tyvek envelope. Blood and marrow should be shipped in a shipping container with an Exempt Human Specimen label.

15.2.3 Labeling and Shipping

MRD specimens should be sent to the COG Leukemia Biospecimen Bank at Nationwide Children's Hospital. Please see [Sections 15.1.3](#) and [15.1.4](#) for labeling and shipping information.

15.2.4 Research MRD Testing

The requested specimens for this biology study (including paired peripheral blood and bone marrow samples) are additional research-only specimens and results will not be reported back to the treating institution. This research testing will be batched (not performed in real-time) and performed at Hematologics, Inc. (Seattle, WA) or a similar qualified laboratory. RQ-PCR testing for the PML-RAR α transcripts will be performed following EAC standards or per methods with similar or better reliability should new techniques be developed in the future.⁷⁴ The EAC standard testing includes use of 3 separate forward primers to cover the PML breakpoints along with a single reverse primer and probe for the RAR α gene. NCN is calculated as copies PML-RAR α divided by copies control gene ABL. Reportable NCN values will be within a range of 2.000 – 0.001. NCN values outside of this range will be reported as HIGH POSITIVE or LOW POSITIVE. For NCN < 0.0001 results will be reported as NEGATIVE within the quantitative range of this assay. If the specimen failed to amplify the ABL control gene with Ct values > 35 after repeat testing, RNA quality will be deemed inadequate. NB4 cell line cDNA will be used for positive control.

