2.9 PCR Monitoring of Bone Marrow

Quantitative RT-PCR (RQ-PCR) provides several advantages in the diagnosis of APL by providing a very sensitive and specific diagnostic test that establishes the breakpoint specific transcript for monitoring for persistent MRD or for surveillance to detect relapse. A panel of primers that covers the various breakpoints in the PML-RAR α fusion gene transcript is used. An internal housekeeping gene, used to standardize the transcript level and determine the quality of the RNA, decreases false negative results.³³ Thus, PCR testing has become the “gold standard” for confirmation of the diagnosis of APL.³⁴ PCR testing can confirm the presence of the PML-RAR α fusion gene and distinguishes this common type of APL from other rare variants (e.g., PLZF-RAR α) that may not respond to ATRA treatment and should not be included on clinical trials utilizing ATRA as an essential component of therapy. The PCR testing is a very sensitive assay for detection of the

PML-RAR α fusion gene transcript, which allows for detection of MRD and molecular relapse (the latter is recurrent disease detected by PCR prior to signs of full hematologic relapse).

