10.2.2 Molecular Remission

- Molecular remission is the absence of PML-RAR α fusion transcript by RQ-PCR (with an assay sensitivity of at least 10^{-4}) in a bone marrow specimen obtained after at least 14 weeks of Consolidation therapy. A positive test (detectable PML-RAR α fusion transcripts) must be confirmed by a repeat test on a separate bone marrow specimen obtained at least 1 to 2 weeks later.

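### Section 15.2.4 lets the research MRD assay report NEGATIVE (NCN < 0.0001) from RNA too weak to support that call, because it sets an ABL Ct cut-off but no minimum ABL copy number

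*Combined protocol and SAP*

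**What the plan says.** Section 15.2.4 measures residual disease as a normalized copy number (NCN): PML-RARα copies "divided by copies control gene ABL". It then sets the reporting scale. "Reportable NCN values will be within a range of 2.000 – 0.001"; values outside that range are labelled high or low positive; and "For NCN < 0.0001 results will be reported as NEGATIVE within the quantitative range of this assay".

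The one criterion it states for rejecting a sample is on the cycle scale: "If the specimen failed to amplify the ABL control gene with Ct values > 35 after repeat testing, RNA quality will be deemed inadequate". Samples with an ABL Ct up to 35 are therefore accepted. The section refers to EAC standards, or methods at least as reliable. It states no minimum ABL copy number, no detection limit per sample, and no rule for a sample in which ABL is weak and no PML-RARα is seen.

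Section 2.9 explains what the control gene is for: "An internal housekeeping gene, used to standardize the transcript level and determine the quality of the RNA, decreases false negative results".

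Three places govern how the results are used:

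- Section 2.10.2 plans to relate end-Induction NCN, its log-fold reduction from diagnosis, and clearance in marrow and blood to outcome. It hopes that a low value could identify patients for less treatment and monitoring in future studies.
- Section 9.4.2 contains the only formal test: a log-rank comparison of DFS between end-Induction NCN below 1 and NCN of 1 or more.
- Section 15.0 says the research results are batched and play no part in treatment decisions.

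**The concern.** The NEGATIVE limit is set on the NCN scale and the adequacy rule on the Ct scale, and nothing links them. The lowest NCN a sample can show depends on how much ABL it contains. A weak sample with no visible transcript has shown only that NCN is below its own detection limit, which may lie far above 0.0001. Under the rule as written it still receives the same label as a sample with ample RNA.

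What is at stake is the exploratory work under Aim 1.2.2. Unsupported NEGATIVE calls would place some patients with residual disease in the best-response category. They would credit log-fold reductions that were never observed and distort clearance curves. They could also create apparent disagreement between paired blood and marrow samples that differ only in ABL content. Section 2.10.2 gives a negative or low end-Induction result particular weight, and Section 2.9 expects PCR-positive disease on Day 43 of Consolidation Cycle 2 to be rare, so the meaning of NEGATIVE matters at both time points.

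**Working it through.** **The plan's own figures.** The NEGATIVE limit is a rule with no derivation, so there is nothing to reproduce. The inputs to the related DFS test in Section 9.4.2 do reproduce: ln(0.58)/ln(0.90) = 5.17 (stated 5.2), and 150 × 0.90 × 0.65 = 87.75 patients (stated as at least 85).

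**Inputs from Section 15.2.4.** NCN = PML-RARα copies / ABL copies; NEGATIVE if NCN < 0.0001; ABL accepted up to Ct 35.

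**Assumed, because no standard curve is given.** A single copy crosses the threshold at Ct1 = 36 to 45; amplification per cycle E = 2, with 1.9 as a check.

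**Step 1. ABL copies needed for NEGATIVE.** The smallest non-zero NCN is 1/(ABL copies). Setting this to 0.0001 gives 1/0.0001 = 10,000 copies. For about 95% detection the expected transcript count must be about 3, since exp(-3) = 0.05, which gives 3/0.0001 = 30,000 copies. This step uses only the plan's definition.

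**Step 2. What a Ct-35 sample contains.** ABL copies = E^(Ct1 - 35). Chance of seeing no transcript = exp(-NCN × ABL copies). With E = 2:

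| Ct1 | ABL copies at Ct 35 | Lowest NCN (1/copies) | Multiple of 0.0001 | Ct at 10,000 copies | Missed at NCN 0.001 | Missed at NCN 0.01 | Missed at NCN 0.1 | Missed at NCN 1 |
|---|---|---|---|---|---|---|---|---|
| 36 | 2 | 0.5 | 5,000 | 22.7 | 99.8% | 98% | 82% | 14% |
| 38 | 8 | 0.125 | 1,250 | 24.7 | 99% | 92% | 45% | 0.03% |
| 40 | 32 | 0.031 | 312 | 26.7 | 97% | 73% | 4% | about 0 |
| 42 | 128 | 0.0078 | 78 | 28.7 | 88% | 28% | about 0 | about 0 |
| 45 | 1,024 | 0.00098 | 10 | 31.7 | 36% | about 0 | about 0 | about 0 |

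With E = 1.9 the multiples run from 5,263 down to 16. The chance of missing NCN 1 is 15% at Ct1 36 and 0.1% at Ct1 38.

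**Step 3. What would make the rule adequate.** Ct 35 would mean 10,000 copies only if a single copy crossed at Ct 35 + log2(10,000) = 48.3 (49.3 with E = 1.9).

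**Step 4. Effect on log-fold reduction.** Assume for illustration an NCN of 1 at diagnosis. A non-detected result then demonstrates log10(ABL copies) of reduction: 0.3 logs with 2 copies, 1.5 with 32 and 3.0 with 1,024. NEGATIVE credits more than 4 logs.

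**Step 5. Effect at the planned cut.** The last column shows that a true NCN of 1 is almost never missed at Ct 35, except when the sample holds only 2 ABL copies.

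**The case against.** The strongest objection is that the planned test is not harmed. Section 9.4.2 cuts at 1 NCN. A patient with a true NCN of 0.01 belongs in the lower group whether the report reads positive or NEGATIVE. This stands: for the powered comparison the problem is negligible in all but the most extreme assumed case.

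Second, the size rests on an assumed curve. This also stands, and it is why the shortfall is given as a range from 10-fold to 5,000-fold. The direction does not depend on the choice within the assumed range.

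Third, the EAC reference might bring in a control-gene floor. It might, but none is written in the documents, and Section 15.2.4 states its own adequacy rule and allows other methods. Nor does calling NEGATIVE a result within the quantitative range rescue it. That range ends at 0.001, which already needs 1,000 ABL copies, and Ct 35 reaches that only at the most favourable assumed curve.

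Three stronger readings are tempting, and the documents do not support them:

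- **Degraded samples in general are scored as the best responses.** Samples above Ct 35 are rejected, and higher-level disease still reads positive. Only accepted samples with weak ABL and low residual disease are affected, and nothing shows how many there will be.
- **The research assay breaches Section 10.2.2.** The phrase "with an assay sensitivity of at least" there belongs to the definition of molecular remission. Sections 3.1.4.1 and 7.1 assign that assessment to the separate clinical RQ-PCR.
- **Lax storage makes the problem worse.** Section 15.2.2 says "Samples may be stored at room temperature", whereas Section 15.1.2 says "Samples may be stored at room temperature if shipped on the day of collection. If stored for longer, please refrigerate". But Section 15.2.3 sends the reader to Section 15.1.4 for MRD shipping, and that text was not in the copy examined, so the absence of a time limit cannot be asserted.

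**Conclusion.** The point holds for the NEGATIVE call. By the plan's own definition the call needs at least 10,000 ABL copies, and the stated Ct rule does not secure them. With a single-copy Ct of 36 to 45 and two-fold amplification, a sample at the acceptance limit falls about 10-fold to 5,000-fold short. At a single-copy Ct of 40, a true NCN of 0.01, which is 100 times the limit, would be missed 73% of the time.

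The consequence is confined to exploratory Aim 1.2.2: the NEGATIVE category, log-fold reduction, clearance kinetics and paired blood-marrow comparison. The DFS comparison at 1 NCN is essentially unaffected, and treatment decisions and the primary endpoint do not use these results. How many patients are involved cannot be said, because the documents give no distribution of ABL Ct. The matter is worth correcting because the remedy is cheap and the NEGATIVE label is meant to inform later treatment reduction.

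**What to change.** In Section 15.2.4:

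1. Report NEGATIVE only when the sample has at least 10,000 ABL copies. This is the minimum: at exactly 10,000 copies a true NCN of 0.0001 is still missed with probability exp(-1) = 37%, so a stricter floor near 30,000 would be needed for 95% detection.
2. Report ABL copies, or the sample's detection limit, with every result.
3. Class a non-detected result with fewer ABL copies as inadequate for a NEGATIVE call. Treat it as left-censored at 1/(ABL copies) in the log-reduction and kinetics analyses.
4. Keep such a sample in the group below 1 NCN for Section 9.4.2 when its detection limit is clearly below 1. By the 3/copies rule, 8 ABL copies give 0.375 and qualify; 2 copies give 1.5 and do not.

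If the EAC standard is meant to supply an ABL floor, that number should be written into the section.

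The cost is small. ABL copies are already needed to compute NCN, no new assay or visit is required, and batched testing lets the rule be fixed before analysis. The downside is that some low-quality samples lose their NEGATIVE label. No change to sample storage is proposed.
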